**HISPANIC CLINIC DAY FLOW CHART**

*Consent:*

Written informed consent will be obtained for all participants by the research assistant in person at MWCHC [**see attached consent**].

*Baseline Assessment:*

Immediately following consent, all participants will complete a baseline assessment (English or Spanish according to participant preference) to collect demographic information, trust in healthcare system assessment, and health literacy assessment [**see baseline survey**]. This assessment will be collected by paper and pencil with the help of the research assistant.

*Randomization:*

Women will be randomized to the control arm, the intervention arm 1 (individual education), or the intervention arm 2 (group education) immediately following consent. Randomization will be performed using the random number generator software available in the R statistical package ([www.r-project.org](http://www.r-project.org)).

*Control Arm:*

Immediately following consent and completion of the baseline assessment, women in the control arm will receive standard of care well woman screening. The control arm will receive screening results per MWCHC protocol.

*Intervention Arm 1:*

Immediately following consent and completion of the baseline assessment, women in the intervention arm 1 will participate in a 20-30 minute educational session [**see educational slides**] alone with the PN. Well woman screening will follow the educational session. The PN will be available to assist with questions and language interpretation as necessary. After standard delivery of screening results, the PN will contact these participants to answer any questions about their screening results and to assist with scheduling any additional tests necessary.

*Intervention Arm 2:*

Immediately following consent and completion of the baseline assessment, women in the intervention arm will participate in a 20-30 minute group educational session [**see educational slides**] from the PN. Well woman screening will follow the educational session. The PN will be available to assist with questions and language interpretation as necessary. After standard delivery of screening results, the PN will contact these participants to answer any questions about their screening results and to assist with scheduling any additional tests necessary.

*Post Assessment 2-5 Days After Delivery of Results:*

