Descriptive statistics will be used to analyze the demographic characteristics of participants. Comparison of knowledge in baseline and post assessments will be assessed with  $\chi^2$ , Student *t* tests and Fischer exact tests as necessary. Open-ended responses will be analyzed qualitatively. Post assessment comparison between “intervention” and “control” groups will be assessed with  $\chi^2$ , Student *t* tests and Fischer exact tests as necessary. Open-ended responses will be analyzed qualitatively.

*Sample Size:*

For this pilot study, the proposed sample size of 50 patients/group provides at least 80% power to detect a 29% improvement of the success rate, i.e. 40% vs 69%, with 2 sided Type 1 error = 5%. This calculation was based on the Chi squared test with the normal approximation correction for continuity.

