**Secondary Outcome:**

Assessment of PN impact on Hispanic women’s measures of satisfaction with communication when compared to those receiving standard of care treatment in the screening mammography setting.

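### Communication satisfaction is to be compared between arms by unadjusted tests, although health literacy and language are available at baseline; the tests are valid but may give up some precision

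*Combined protocol and SAP*

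**What the plan says.** The Secondary Outcome section names the effect of the Promotora Navigator (PN) on Hispanic women's "measures of satisfaction with communication when compared to those receiving standard of care treatment in the screening mammography setting". The Primary Outcome is an association between trust and engagement, so this is the only comparison between randomised arms in the outcome list.

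Statistical Considerations begins with "Descriptive statistics will be used to analyze the demographic characteristics of participants". The sentence that governs this point comes later in the same paragraph: the post-assessment comparison of intervention and control uses chi-squared, Student t and Fisher exact tests as needed. No regression model, covariate or stratified analysis is named.

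The Baseline Assessment is completed in English or Spanish as the woman prefers, and serves "to collect demographic information, trust in healthcare system assessment, and health literacy assessment". Item Development names the health literacy scale and places the communication measure in the post assessment only. For both intervention arms the plan adds: "The PN will be available to assist with questions and language interpretation as necessary".

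The Randomization section names the random number generator in R and mentions no stratification or blocking. Sample Size rests on "the proposed sample size of 50 patients/group" and states: "This calculation was based on the Chi squared test with the normal approximation correction for continuity".

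**The concern.** The most useful covariate for a post-intervention score is usually its own baseline value. Communication satisfaction has none, because it concerns care not yet received. Health literacy and language are the natural substitutes: both plausibly relate to how a woman rates communication, and both are fixed before the education session. The investigators already treat literacy as relevant, since Objective 2 relates it to engagement, yet it has no role in the arm comparison.

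If these variables predict the score, an unadjusted analysis leaves explainable variance in the error term and the interval is wider than it need be. If the arms also differ by chance in language or literacy, nothing in the plan says whether or how to adjust. That choice would then be made after the data are seen.

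**Working it through.** **1. The plan's own figure.** Inputs from Sample Size: 40% v 69%, two-sided 5%, 50 per group, continuity-corrected chi-squared.

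- Pooled proportion (0.40 + 0.69)/2 = 0.545. Standard error under the null: sqrt(2 × 0.545 × 0.455/50) = 0.0996. Under the alternative: sqrt((0.24 + 0.2139)/50) = 0.0953.
- Corrected normal approximation: (0.29 − 0.02 − 1.96 × 0.0996)/0.0953 = 0.785, which gives power 78.4%.
- Exact enumeration of the corrected test gives 80.0%. The corrected formula asks for 52 per group.

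The stated size reproduces within tolerance. It concerns a binary outcome and an unadjusted test.

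**2. Model for the gain.** Take a continuous communication score, 50 per group, two covariates, N = 100. The documents give no R2, so a range is assumed.

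- Variance ratio, adjusted to unadjusted: (1 − R2) × (1 + 2/95). The second factor, 1.021, is the cost of estimating two covariates.
- Unadjusted t test: power is 80.0% at a difference of 0.566 SD, since 0.566/sqrt(2/50) = 2.83.
- Adjusted: the same difference divided by sqrt(2/50 × variance ratio), on 96 degrees of freedom.

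| R2 (assumed) | Variance ratio | Interval width v unadjusted | Power at 0.566 SD |
|---|---|---|---|
| 0 | 1.021 | 1.01 | 79.2% |
| 0.02 | 1.001 | 1.00 | 80.0% |
| 0.05 | 0.970 | 0.98 | 81.2% |
| 0.10 | 0.919 | 0.96 | 83.2% |
| 0.25 | 0.766 | 0.88 | 89.3% |

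Break-even is where (1 − R2) × 1.021 = 1, an R2 of about 0.02. At R2 0.10 and 0.25 the gain equals 1/0.919 − 1 = 9% and 1/0.766 − 1 = 31% more women.

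**3. What language alone might supply.** Assume 80% prefer Spanish and language shifts the score by 0.5 SD. It then explains 0.8 × 0.2 × 0.5² = 0.04 of the variance. Net of the 2% cost the gain is about 2%, so anything larger must come from literacy.

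**4. Chance imbalance under the same assumptions.** The arm difference in Spanish preference has SD sqrt(2 × 0.8 × 0.2/50) = 0.08. The resulting shift in the estimate has SD 0.5 × 0.08 = 0.04 score SD, with 95% limits of about ±0.08. The standard error of the arm difference is sqrt(2/50) = 0.20 SD.

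**5. Dependence on the design.** The 50 per group comes from Sample Size. The Randomization section allocates to three arms, a separate inconsistency. If that split is equal and the two intervention arms are pooled, the standard error is sqrt(1/33 + 1/67) = 0.213 SD rather than 0.20. Unadjusted power is then below 80%, but the variance ratios in the table are unchanged.

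**The case against.** The strongest reply is that nothing here is invalid. The t, chi-squared and Fisher comparisons keep their type I error and are unbiased over randomisation, and chance imbalance is already counted in the standard error. In a 100-woman pilot, leaving covariates out is a defensible choice, and the gain could be near zero if almost all women prefer Spanish or literacy predicts the score weakly. All of this stands, and it limits the point to efficiency and pre-specification. It does not remove the point, because the loss from adjusting on useless covariates is smaller than the gain at even a modest R2.

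A reader might infer more than the documents support:

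- **That splitting by language would separate an interpreter effect from a wider navigator effect.** It would not. Spanish-preferring women in the intervention arms receive education, interpretation and result follow-up together. Main-effect adjustment does not address this either. With 20% English-preferring (assumed), about 10 per arm, the English-stratum interval is about ±1.96 × sqrt(2/10) = ±0.88 SD.
- **That baseline data serve only description.** Statistical Considerations also plans tests of baseline against post assessment, and the objectives use trust and literacy as predictors of engagement.
- **That the gain is free.** Estimating two covariates costs about 2% of variance.
- **That route of recruitment belongs in the model.** The documents give no reason to think it predictive.

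Two cautions also stand. Language preference is not listed in the text as a recorded variable; it is inferred from the form used, and the survey itself is not shown. The power figures use a continuous score, whereas the plan's calculation is for a success rate.

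**Conclusion.** The point holds as a modest improvement in efficiency. The plan compares a post-only outcome without using two baseline variables that are available before the intervention. On a continuous score with two groups of 50, adjustment takes power at 0.566 SD from 80% to between 81% (R2 0.05) and 89% (R2 0.25). The worst case, with no prognostic value, is 79.2%.

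These figures rest on assumed R2 values, a linear model with two covariates, and the two-group size in the Sample Size section. The only language inputs tried here imply an R2 of about 0.04, so the lower end of the range is the safer expectation unless literacy is clearly predictive. The documents do not support a claim that the planned tests are biased, or that the stated sample size is wrong on this account.

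**What to change.** State in Statistical Considerations that communication and satisfaction scores will be compared between arms by linear regression adjusted for baseline health literacy and language of the baseline assessment. The adjusted mean difference and its 95% interval would be the main result. For binary items, report a covariate-standardised risk difference. Keep the planned unadjusted comparison as a supporting analysis.

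The cost is SAP wording, two degrees of freedom, and recording the form language as a field if the survey does not already capture it. No new instrument or contact is needed. Fixing the covariates now also avoids choosing them after any imbalance has been seen.

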**Brief Overview/Objectives:**

1. To assess the relationship between level of trust in the healthcare system and active engagement in a mammography screening program in the local Hispanic population.
2. To assess the relationship between health literacy and active engagement in a mammography screening program in the local Hispanic population.
3. To determine whether a Promotora Navigator improves Hispanic women's measures of trust in the healthcare system and provider compared to those receiving standard of care treatment in the screening mammography setting.
4. To determine whether a Promotora Navigator improves Hispanic women's measures of satisfaction with communication when compared to those receiving standard of care treatment in the screening mammography setting.

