Do trust in the healthcare system and/or health literacy impact engagement in a screening mammography program in the local Hispanic population? *We hypothesize that higher levels of trust and health literacy are positively related to engagement in a screening mammography program.*

Does a PN improve Hispanic women’s measures of trust in the healthcare system and satisfaction with communication in the screening mammography setting when compared to those receiving standard of care? *We hypothesize that women with access to a PN will have higher levels of trust in the healthcare system and satisfaction with communication than women receiving the standard of care.*

Methods:

*Study Design:* The study design is a randomized control trial. In this pilot study, 100 participants will be randomized to either a) the intervention, in which they receive care from the PN or b) the control, in which they receive the standard of care.

*PN Identification and Education:*

A PN will be identified and trained by [name], VICC Community Health Educator. [name] will supplement educational materials.

*Inclusion/Exclusion Criteria:*

Inclusion criteria will be Hispanic women meeting United States Preventive Services (USPSTF) criteria for screening mammography and criteria for clinical service coverage through the TN Breast and Cervical Cancer Screening Program.

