All participants will be contacted via telephone by the bilingual research assistant 2 -5 days after results are distributed by standard method for post assessment. This will be conducted in English or Spanish according to participant preference. This post assessment will repeat the measures of trust. It will also assess measures of satisfaction with care, satisfaction with communication, relationship with the promotora and intent to follow-up [**see attached post assessment**]. After the post

assessment, the existing Vanderbilt Ingram Cancer Center (VICC) Breast and Cervical Cancer pamphlet [**see attached VICC Breast and Cervical Cancer pamphlet**].

*Delayed Chart Review:*

The bilingual research assistant will perform delayed chart review 2-4 weeks following delivery of results to assess whether patients needing follow-up diagnostic studies returned. Delayed chart review may also occur in 2-3 years to assess adherence to continued screening.

*Data Collection:*

Baseline assessment data will be collected by paper and pencil (in Spanish or English language per patient request) immediately following consent at MWCHC. The bilingual research assistant will be available to assist as necessary. Post assessment data will be collected electronically in REDCap by bilingual research assistant via telephone. Return for Follow-Up data will be accessed via patient medical record. Data will be stored in a REDCap.

*Item Development:*

**Baseline Assessment:** The baseline assessment will collect demographic information. Additionally, the baseline assessment will assess trust in the healthcare system using the Healthcare System Distrust Scale and health literacy using the Self-Reported Health Literacy Scale.

**Post Assessment:** Measures of healthcare system distrust will be repeated in the post assessment. The post assessment will include multiple items to assess satisfaction with care using the Patient Satisfaction with Cancer Scale, satisfaction with communication adapted from the Interpersonal Processes of Care Survey, and satisfaction with the promotora. The post assessment will also assess intent to follow up.

*Statistical Considerations:*

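### The pre/post analysis names a variable that neither described assessment contains and specifies no paired method, and the trust comparison between arms ignores the baseline distrust score

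*Combined protocol and SAP*

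**What the plan says.** Statistical Considerations has one sentence on change over time: "Comparison of knowledge in baseline and post assessments will be assessed with" chi-squared, Student t "tests and Fischer exact tests as necessary". The next analysis sentence covers the arms: "Post assessment comparison between “intervention” and “control” groups will be assessed with" the same three tests. No paired test, change score or baseline-adjusted model is named.

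The assessments are described elsewhere in the protocol. The Baseline Assessment paragraph says the form is "to collect demographic information, trust in healthcare system assessment, and health literacy assessment". Under Item Development the plan says "Measures of healthcare system distrust will be repeated in the post assessment". The other post-assessment content is satisfaction with care and with communication, the relationship with the promotora, and intent to follow up.

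Objective 3 asks whether the navigator improves "measures of trust in the healthcare system and provider compared to those receiving standard of care treatment".

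The number of arms also differs between sections. Study Design has two: "100 participants will be randomized to either a) the intervention, in which they receive care from the PN or b) the control". The Randomization paragraph has three: "Women will be randomized to the control arm, the intervention arm 1 (individual education), or the intervention arm 2 (group education").

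**The concern.** There are three linked problems.

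- **The variable.** The pre/post sentence names knowledge, while the measure described as repeated is distrust. A reader cannot tell what will be tested, or whether change in distrust will be tested at all.
- **The method.** Two scores from the same woman are correlated. Chi-squared and Fisher exact tests, and the two-sample t test, treat them as independent. That overstates the standard error of the change when the correlation is positive.
- **The trust comparison between arms.** Baseline distrust is to be collected from every participant before care starts, and it is likely to predict her later score. A post-only comparison discards that information. What is at stake is precision and protection against chance baseline imbalance in a 100-woman pilot, not validity.

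**Working it through.** **The plan's own figure.** The Sample Size paragraph gives 50 per group and at least 80% power for 40% v 69%, two-sided 5%, with continuity correction.

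- Mean proportion = (0.40 + 0.69)/2 = 0.545.
- Uncorrected n = [1.96·√(2·0.545·0.455) + 0.8416·√(0.40·0.60 + 0.69·0.31)]² / 0.29² = 45.1, so 46 per group.
- Corrected n = (45.1/4)·[1 + √(1 + 4/(45.1·0.29))]² = 51.8, so 52 per group.
- Power at 50 per group is 78.4% corrected and 84.0% uncorrected.

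The stated figure is reproduced to within 2 patients and 2 points and is not in dispute. It concerns a binary success rate in two independent groups, so it says nothing about a repeated distrust score.

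**Matching the variable to the forms.**

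| Measure | Baseline | Post |
|---|---|---|
| Demographics | yes | – |
| Healthcare system distrust | yes | yes |
| Health literacy | yes | – |
| Satisfaction with care, satisfaction with communication, relationship with promotora, intent to follow up | – | yes |
| Knowledge | – | – |

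Health literacy is the nearest item to knowledge, but it is a different construct and is not described as repeated.

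**Assumptions for what follows.** The documents give no SD, no baseline-post correlation r and no trust effect. I take r = 0.3, 0.5 and 0.7, equal SDs at both times, a between-arm effect of 0.5 SD, independent women and no loss to follow-up.

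**Pre/post, if unpaired tests were used on distrust.** The true standard error is SD·√(2(1−r)/n), and the unpaired one is SD·√(2/n). Their ratio is 1/√(1−r), and the actual two-sided alpha is 2·[1 − Φ(1.96 × ratio)].

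| r | SE ratio | Actual alpha |
|---|---|---|
| 0.3 | 1.20 | 1.9% |
| 0.5 | 1.41 | 0.6% |
| 0.7 | 1.83 | 0.03% |

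Simulation of 40,000 trials with 100 pairs gave 2.0%, 0.7% and 0.04%. The error is conservative. For an assumed 0.3 SD change within one arm of 50, power by normal approximation would be 29%, 26% and 20% unpaired, against 43%, 56% and 78% paired.

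**Between arms, Objective 3.** Adjusting for baseline multiplies the residual variance by 1−r² = 0.91, 0.75 and 0.51. That is equivalent to 100/(1−r²) = 110, 133 and 196 women in place of 100. Power uses the noncentral t distribution, with one degree of freedom spent on the covariate. The noncentrality is 0.5/√(1/n₁ + 1/n₂), divided by √(1−r²) when adjusted.

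- 50 v 50: 0.5/0.200 = 2.50 unadjusted, and 2.62, 2.89 and 3.50 adjusted.
- 67 v 33 (three equal arms assumed, the two intervention arms pooled): 0.5/0.2127 = 2.35 unadjusted, and 2.46, 2.72 and 3.29 adjusted.

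| Split | Post only | r = 0.3 | r = 0.5 | r = 0.7 |
|---|---|---|---|---|
| 50 v 50 | 69.7% | 73.7% | 81.5% | 93.4% |
| 67 v 33 | 64.4% | 68.4% | 76.7% | 90.3% |

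**Chance imbalance, 50 v 50.** The SD of the baseline difference is √(1/50 + 1/50) = 0.20 SD. About 1 trial in 20 therefore exceeds 1.96 × 0.20 = 0.39 SD in either direction. A difference of that size shifts the expected post-only difference by r × 0.392 = 0.12, 0.20 or 0.27 SD.

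**The case against.** Only the stray variable name is a plain textual defect, and even that is provisional. Both questionnaires are attachments outside the documents, and the intervention is an educational session, so knowledge items are plausible. That stands, and the claim is limited to the content as described. If the forms do contain such items, the descriptions need completing instead.

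Student t may include the paired form. That also stands: the alpha figures show what would follow if unpaired tests were used, not what the plan commits to. They are applied to distrust, which the sentence does not name, and the plan does not say whether the comparison is pooled or by arm.

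Post-only comparison is unbiased, the trial is a pilot, and Objective 3 is not among the listed outcomes. All true, and this limits the weight of the point. But precision is scarce with 100 women, and Objective 3 is still a stated objective and hypothesis.

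The gain is uncertain. Baseline is on paper and post is by telephone, so a high r cannot be taken for granted. Loss to follow-up, or correlation among women taught in groups, would lower every power figure. Chance imbalance is largely the same loss seen within a single trial, since the unadjusted standard error already allows for it, so the two should not be added together. None of this removes the case for adjustment.

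**Conclusion.** The concern holds in all three parts. The pre/post sentence names a variable absent from both assessments as described. No paired method is specified. The trust comparison leaves the baseline distrust score unused.

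The wording mismatch is certain on the text. The size of the loss is conditional on the assumed r and effect: 4 points of power at r = 0.3, about 12 at r = 0.5 and about 24 at r = 0.7 with 50 v 50. There is no bias and no inflation of false positives. The listed primary outcome (trust and engagement) and secondary outcome (satisfaction with communication) are unaffected. It should be put right before the data are analyzed.

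**What to change.** 1. In the pre/post sentence, replace knowledge with the Healthcare System Distrust score. If the questionnaires do contain knowledge items, list them in the assessment descriptions.
2. For Objective 3, specify ANCOVA: post distrust on arm, adjusted for baseline distrust. Define arm first, by reconciling the two groups of Study Design with the three of Randomization and stating whether the intervention arms are pooled. The arm count is a wider matter, but this model cannot be written without it.
3. Report within-woman change descriptively, with a paired t test for scores and McNemar's test for binary items.
4. Keep t, chi-squared and Fisher exact tests for measures taken once.

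Objective 3 also names trust in the provider, for which no separate instrument is described. This ANCOVA covers system distrust only.

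The cost is two rewritten sentences and the reconciliation of the arms. Baseline distrust is already to be collected, so no new data or visits are needed.

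### Student's t test is dependable only if group sizes or SDs are about equal, and the three-arm randomisation text leaves the 50 v 50 split unsecured; naming Welch's test is a cheap safeguard

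*Combined protocol and SAP*

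**What the plan says.** Statistical Considerations plans two groups: "Post assessment comparison between “intervention” and “control” groups will be assessed with" chi-squared tests, Student t "tests and Fischer exact tests as necessary". It does not say whether the t test pools the variances, and it mentions neither a variance check nor an unequal-variance version.

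The documents describe the randomised groups in two ways.

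- Methods, Study Design: "100 participants will be randomized to either a) the intervention, in which they receive care from the PN or b) the control". Sample Size agrees: "the proposed sample size of 50 patients/group provides at least 80% power". Together these give 50 v 50.
- Methods, Randomization: "Women will be randomized to the control arm, the intervention arm 1 (individual education), or the intervention arm 2 (group education"). No allocation ratio follows. The only detail is that "Randomization will be performed using the random number generator software available in the R statistical package".

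No section says how three arms become the two groups of the analysis. No SD is given for any scale.

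**The concern.** The pooled-variance t test estimates one common SD, weighted towards the larger group. If the smaller group is the more variable, the standard error is too small and the test rejects too often. If the larger group is the more variable, the test rejects too rarely. With equal group sizes the two errors cancel. The protection therefore comes from the 50 v 50 split, and the three-arm text does not secure that split.

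The affected comparisons are the between-group scores behind objectives 3 and 4, including satisfaction with communication, which is the stated secondary outcome. Their p-values and confidence intervals could be somewhat too optimistic or too conservative, and the direction cannot be known in advance.

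**Working it through.** **The plan's own figure.** Inputs from Sample Size: 40% v 69%, two-sided 5%, 80% power, chi-squared test with continuity correction.

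- Uncorrected: n = [1.96·√(2·0.545·0.455) + 0.8416·√(0.40·0.60 + 0.69·0.31)]² / 0.29² = (1.3803 + 0.5670)² / 0.0841 = 45.1, so 46 per group.
- Corrected: (45.1/4)·[1 + √(1 + 4/(45.1·0.29))]² = 51.8, so 52 per group.
- At 50 per group, power is 78.4% with the correction and 84.0% without.

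The stated 50 per group is thus reproduced to within 2 patients. It rests on a binary success rate, so it gives no SD for the t tests.

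**Group sizes.** The stated size is 50 v 50. Three arms at 1:1:1 with the education arms pooled give 100/3 ≈ 33 control v 67 navigator. Three arms give 50 v 50 only at 2:1:1 (50, 25, 25), a ratio that no section states.

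**Why sizes matter.** Let r be control SD divided by navigator SD, with navigator SD = 1. The true variance of the mean difference is r²/n₁ + 1/n₂. On average, the pooled test uses [((n₁−1)r² + (n₂−1))/(n₁+n₂−2)]·(1/n₁ + 1/n₂).

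- 33 v 67, r = 1.5: true 2.25/33 + 1/67 = 0.0831. Pooled (32·2.25 + 66)/98 = 1.408, times 0.04523 = 0.0637. Ratio 1.305, so the standard error is too small by a factor of √1.305 = 1.142. The effective cut-off is 1.984/1.142 = 1.737, about 8% two-sided.
- 33 v 67, r = 0.67: true 0.4489/33 + 1/67 = 0.0285. Pooled (32·0.4489 + 66)/98 = 0.820, times 0.04523 = 0.0371. Ratio 0.769. The effective cut-off is 1.984/0.877 = 2.26, about 2.4%.
- 50 v 50, any r: both expressions equal (r² + 1)/50, so the ratio is exactly 1.

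**Simulated rejection rates with equal means** (normal data, two-sided 5%, 400,000 replicates per setting; r is an assumption):

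| r | 33 v 67, Student | 33 v 67, Welch | 50 v 50, Student | 50 v 50, Welch |
|---|---|---|---|---|
| 0.67 | 2.6% | 5.0% | 5.0% | 4.9% |
| 0.8 | 3.5% | 5.0% | 5.0% | 5.0% |
| 1 | 5.1% | 5.0% | 5.0% | 5.0% |
| 1.25 | 6.9% | 5.0% | 5.0% | 5.0% |
| 1.5 | 8.6% | 5.0% | 5.1% | 5.0% |

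If the arms were instead compared pairwise at 33 v 33, Student's test would stay at 5.0% to 5.1% over the same ratios.

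**Interval coverage with a real effect.** Assume a score capped at 5 and a shift of 0.4 to 0.5 points before capping (for example SD 1 and control mean 4.0 to 4.3 before capping). The cap reduces the navigator spread, giving r of roughly 1.1 to 1.2. At 33 v 67, Student's 95% interval covers about 93 to 94% and Welch's about 95%.

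**Cost of Welch when the SDs are equal.** At 33 v 67, power falls from 79.8% to 79.3% for a difference of 0.6 SD, and from 75.6% to 75.1% for 0.57 SD. At 50 v 50 and 0.57 SD it is 80.5% with either test.

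**The case against.** The strongest reply is that the only group size the documents state is 50 per group, where Student's test is sound whatever the SDs. Pooling the education arms is an inference from a two-group analysis of three arms. The 33 v 67 split is a further inference, because no ratio is given. The distortion also needs unequal SDs, and no SD is reported. All of this stands, and it makes the point conditional.

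A reader might also infer that the navigator, by moving scores towards a ceiling, would raise the type I error to the 6.9% or 8.6% in the table. That does not follow. The ceiling narrows the spread only if the navigator really shifts scores. If she has no effect at all, randomisation gives both groups the same distribution and Student's test holds its level. The figures that match this mechanism are the coverage figures, a shortfall of about 1 to 2 points.

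Nor do the documents say that the random number generator is used without blocking. If it were, a two-arm 1:1 trial of 100 would end at 45 v 55 or worse about 37% of the time (exact binomial). Even then, Student's test would reject only about 6.0% of the time at r = 1.5.

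Finally, this is a pilot whose stated primary outcome is the relationship between trust and engagement, not this comparison. That limits the importance of the point. It is no reason to keep the less robust test, since the change costs almost nothing and is best made before the data are seen.

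**Conclusion.** The concern holds in conditional form. The plan names a test that relies on equal sizes or equal spread, and its text secures neither. If allocation is 1:1:1, the education arms are pooled, and the SD ratio lies between 0.67 and 1.5 (all assumptions), Student's test rejects about 2.6% to 8.6% of the time with equal means, against about 5% for Welch's. In the capped-score case with a real effect, the interval loses about 1 to 2 points of coverage. At the stated 50 v 50 there is no practical difference.

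A reader might go further and conclude that the planned analysis gives wrong error rates, or that Welch's test is entirely free. The documents do not support the first, because they establish neither unequal sizes nor unequal SDs. The calculation does not support the second: the cost is small but not zero. The firmer defect is the conflict between two arms of 50 and three arms with no ratio. The choice of t test is a cheap improvement on top of that.

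**What to change.** In Statistical Considerations, replace Student's t test with Welch's unequal-variance t test for the between-group comparisons of scores. Suggested wording: *Mean scores in the intervention and control groups will be compared with Welch's unequal-variance t test, with a 95% confidence interval for the difference.*

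Also reconcile Study Design, Randomization and Sample Size: state the number of arms, the allocation ratio, and whether the education arms are combined for the comparison with control.

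The first change alters a few words. It costs about 0.5 percentage points of power at 33 v 67 with equal SDs and essentially none at 50 v 50. The second needs only text, and is required whichever t test is used. Reconciling the arms would not make Welch's test redundant unless the analysed numbers also end about equal. The post-assessment is by telephone and Sample Size makes no allowance for non-response, so that is not assured.
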